The primary outcome is the occurrence of reoperations of any cause within 2 years from the index surgery. The expected reoperation rate in the non-robotic group is likely to be higher than 3-5% over a 2-year period [9–11], and may in the robotic-assisted group be 1% or less [12]. A difference of 2 percentage points or greater is considered clinically meaningful. Power analyses (80% power, α 0.05) have been made in two scenarios, with reoperation rates of 3% vs 1%, or 5% vs 3%. We estimate a ratio of 1:6 for robotic-assisted surgery vs navigation-assisted or free hand surgeries.

Comparing 3% and 1% reoperation rates, 420 robotic-assisted surgery patients and 2,520 non-robotic surgery patients are needed (yielding a total sample size of 2,940 patients). In case reoperation rates are 5% and 3%, 866 robotic-assisted surgery patients and 5,196 non-robotic surgery patients are needed (yielding a total sample size of 6,062 patients). An increased proportion of robotic-assisted surgeries or a larger difference in reoperation rates will decrease the total sample size.

An estimated 1800 patients per year are treated with pedicle screw instrumentation at the hospitals, totaling 7,200 patients in 4 years. If we after 4 years deem that the sample size will not be reached in a reasonable time frame, the study will be stopped.

No patients will be lost to follow-up, as outcomes will be ascertained through linkage with national quality, health and surgical registries, requiring no active participation from patients or clinical teams beyond standard registration. If a patient moves abroad before the 2-year period has come to an end, their existing data will be used.

To reduce confounding by indication in this non-randomized design, we will apply both propensity score matching (PSM) and inverse probability weighting (IPW). The propensity score will be estimated using logistic regression, incorporating relevant baseline covariates including age, sex, BMI, smoking status, diagnosis, number of levels fused, revision status, surgical approach (minimally invasive vs. open), interbody device use, and fixed effects for hospital site.

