In the primary analysis, 1:2 nearest-neighbor matching without replacement will be used, with a caliper of 0.2 standard deviations of the logit of the propensity score. Covariate balance after matching will be evaluated using standardized mean differences (SMDs), with $SMD < 0.1$ considered acceptable. Outcome analysis will be performed using Cox proportional hazards regression with robust standard errors to account for matched pairs.

As a secondary analysis, IPW will be used to create a pseudo-population in which treatment assignment is independent of observed covariates. Stabilized weights will be applied, and outcome analysis will be conducted using weighted regression models, adjusted for baseline covariates to enhance robustness.

Although both methods are suitable for dealing with moderate imbalances in group size, it is important to note that reducing the size of the non-robotic group may limit the number of matches available during PSM and could increase variance in the IPW analysis if extreme weights arise. These risks will be mitigated through careful diagnostics, including evaluation of match yield, standardized mean differences, and weight distributions. Overlap weighting or trimming will be considered if weight instability is detected.

While the study is powered at 80% based on the reduced cohort, adjusted analyses using propensity score methods may yield a slightly reduced effective sample size due to matching inefficiency or variance inflation. However, both approaches are expected to preserve sufficient power to detect the prespecified effect size, given the projected event rate and available sample size.

Multiple imputation will be used to handle missing baseline data, and all patients will be included in the final analysis. An increased proportion of robotic surgeries relative to non-robotic surgeries will decrease the overall sample size requirement to detect the same effect.

Secondary outcome - Screw placement precision

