Patient reported outcomes will be collected through the Swedish Spine Register (Swespine) and the Swedish Fracture Register (SFR). Response rates at 1 year is around 75-80%. Response rates in the SFR are lower. The majority of patients will be registered in Swespine (only fracture patients are registered in the SFR). Depending on diagnoses different questionnaires are used. The only questionnaires in Swespine and SFR that are distributed irrespective of diagnoses are EQ-VAS running from 0 (worst) to 100 (best possible health) and EQ-5D. Other questionnaires are Oswestry Disability Index (ODI), Scoliosis Research Society-22revised (SRS-22r), Early Onset Scoliosis Questionnaire-24 (EOSQ-24) and Short Musculoskeletal Function Assessment (SMFA), but are only answered by subpopulations. Several studies indicate that 2 year data does not result in additional information compared to 1 year data, so our primary analysis will use 1 year data, which are available in both Swespine and SFR.

Continuous outcome analysis

EQ-VAS will be analyzed as a continuous variable. We consider a 5-point difference between groups as clinically relevant at the group level, corresponding to a small-to-moderate effect size (Cohen's d appr. 0.25), with an expected standard deviation of 20 points, power 80% and α

0.05. The minimum required number of answering patients in the robotic-assisted group would be 147 and in the non-robotic-assisted group 882. We will exceed this number and achieve a quite reliable estimate if all patients are included in this analysis, also when considering that 30%-40% may not respond to questionnaires in Swespine and SFR.

PASS (Patient Acceptable Symptom State)

We will report the proportion of patients reaching a Patient Acceptable Symptom State (PASS), defined as EQ-VAS ≥ 75 for elective cases and ≥ 65 for non-elective cases. A PASS threshold of 10 percentage point difference in the proportion achieving PASS is considered meaningful. The minimum required number of answering patients in the robotic-assisted group would be 226 and in the non-robotic-assisted group 1,356 if power is 80% and α 0.05. We expect the sample size to provide sufficient power to detect any difference.

15. Recruitment

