Patients will be included consecutively at each site during the enrollment window which is planned to be four years (2025–2029). Currently robotic-assisted spine surgery is available in two hospitals (Umeå and Örebro), with a third hospital waiting for their equipment to be installed (Uppsala). If other hospitals install robotic-assisted surgery during the study period this will just result in more patients involved in the robotic-assisted arm of the trial, which would result in a potentially faster inclusion of the needed amount of patients. We still believe that during the study period more patients will be operated with non-robotic-assisted methods than with robotic-assisted methods.

16–17. Allocation and blinding

No randomization or blinding will be performed. If a planned robotic-assisted surgery is abandoned after the start of surgery, the patient will be included in the robotic-assisted group (i.e. intention to treat principle).

18. Data collection methods

Data will be collected through national registries (Swespine, the Swedish Fracture Register, the Swedish PeriOperative Register, hospital systems (electronic health records, surgical planning software, Picture Archiving and Communication System; PACS and others). PROMs will be recorded preoperatively, and at follow-ups (Swespine: 1, 2 and 5 years; the Swedish Fracture Register: 1 year). Images will be retrieved using standardized CT protocols and assessment will be made by at least two researchers independently.

19. Data management

Data will be collected and managed in compliance with GDPR. Regular validation and updates will occur every 6–12 months. Final datasets will be stored at Uppsala University for a minimum of 15 years.

20. Statistical methods

Statistical analysis will compare outcomes using appropriate parametric or non-parametric tests,

including survival methods. Baseline characteristics will be adjusted for using multivariable models. Adjustment variables include age, diagnosis, comorbidities, previous spine surgery, number of levels, number of screws, robotic system type, use of navigation or free-hand surgery and hospital.

Analysis is currently planned to be performed in R. Interim analyses will be performed when half of the patients have been included. Sensitivity analyses will be performed as described earlier.

21. Data monitoring

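### The propensity score for the primary reoperation analysis does not name comorbidity, which Section 20 lists, and neither list names calendar time although robots arrive during enrolment

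*Protocol*

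**What the plan says.** For Substudy 3, Section 14 estimates the propensity score by logistic regression, "incorporating relevant baseline covariates including age, sex, BMI, smoking status, diagnosis, number of levels fused, revision status", and then "surgical approach (minimally invasive vs. open), interbody device use, and fixed effects for hospital site". That score drives the primary analysis, in which each robotic patient is matched to two controls. Balance is judged by standardized mean differences (SMD) below 0.1. The model after matching is described in one sentence: "Outcome analysis will be performed using Cox proportional hazards regression with robust standard errors to account for matched pairs". The weighted analysis, which is secondary, is additionally adjusted for baseline covariates.

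Section 20 gives a different set for multivariable adjustment: "Adjustment variables include age, diagnosis, comorbidities, previous spine surgery, number of levels, number of screws, robotic system type", and after that navigation or freehand use and hospital.

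Section 15 plans four years of enrolment. Two hospitals have a robot, a third is waiting for its installation, and others may follow.

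For patient-reported outcomes, Section 14 states that "EQ-VAS will be analyzed as a continuous variable" and gives no model. Section 18 states that "PROMs will be recorded preoperatively, and at follow-ups".

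**The concern.** In a non-randomized comparison the primary result is only as good as the set of variables used to make the groups comparable. By naming comorbidity in Section 20, the sponsor treats it as something to adjust for. Yet it is missing from the named list that decides the primary reoperation result. Calendar time is on neither list, although the installation schedule makes the chance of robotic surgery depend on when a patient was operated on.

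The outcome is reoperation for any cause and the target difference is 2 percentage points, so a modest residual imbalance could be a noticeable part of the estimate. The SMD check offers no protection if it is applied only to the listed covariates, because a variable that is not listed is not checked.

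**Working it through.** **1. The plan's own figures.** The sample sizes reproduce and do not depend on the covariate list. They are not in dispute.
- EQ-VAS (5-point difference, SD 20, two-sided 0.05, 80% power, 1:6): n = (1.96 + 0.8416)² × 20² × (1 + 1/6) / 5² = 146.5, so 147 robotic and 6 × 147 = 882 non-robotic, as stated.
- Reoperation: the arcsine formula n = (1.96 + 0.8416)² × (1 + 1/6) / h², with h = 2·asin√p₀ − 2·asin√p₁, gives 420 for 3% vs 1% and 866 for 5% vs 3%, as stated.

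**2. The two lists side by side.**

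| Variable | Section 14 propensity score | Section 20 |
|---|---|---|
| Age, diagnosis, levels, hospital | named | named |
| Revision status / previous spine surgery | named | named |
| Sex, BMI, smoking, approach, interbody device | named | not named |
| Comorbidity | not named | named |
| Number of screws | not named | named |
| Robotic system type; navigation or freehand | not named | named |
| Calendar time of surgery | not named | not named |
| Preoperative EQ-VAS | not named | not named |

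**3. Does the outcome model fill the gap?** The matched Cox model states robust standard errors and no covariates. Covariate adjustment is stated only for the secondary weighted analysis. Section 20 is not tied to the matched analysis.

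**4. Calendar time.** Hospital fixed effects absorb constant differences between hospitals. They do not absorb change within a hospital. Where a robot is installed during enrolment, robotic patients treated afterwards can be matched to controls treated before. Any drift in reoperation risk over the period then enters the treatment effect. The date of surgery is necessarily known, since the outcome is timed from index surgery.

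**5. Size for comorbidity.** The documents give neither prevalence by arm nor a risk ratio, so these are assumptions. With no true treatment effect, an unbalanced binary factor that is independent of the matched covariates produces

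spurious ratio = [1 + p_R(RR − 1)] / [1 + p_C(RR − 1)],

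where p_R and p_C are its prevalence in the robotic and control groups. At a 5% control rate the spurious difference is 5 × (1 − ratio) points.

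| RR | p_R / p_C | Ratio | Points at 5% |
|---|---|---|---|
| 1.5 | 25% / 30% | 1.125/1.150 = 0.978 | 0.11 |
| 2.0 | 20% / 30% | 1.20/1.30 = 0.923 | 0.38 |
| 2.5 | 20% / 40% | 1.30/1.60 = 0.8125 | 0.94 |
| 3.0 | 20% / 40% | 1.40/1.80 = 0.778 | 1.11 |

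At a 3% rate the first and last rows become 0.07 and 0.67 points. Age, BMI, smoking and diagnosis are already matched and would absorb part of this, so the figures lie toward the upper end. If comorbidity were commoner in the robotic group, the sign would reverse.

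**6. Preoperative EQ-VAS.** The stated 147/882 is an unadjusted two-group calculation. Assume a correlation ρ of 0.3 to 0.6 between baseline and 1 year, with equal SDs so that the slope equals ρ. An unadjusted 5-point baseline imbalance then carries 5ρ = 1.5 to 3.0 points into a comparison where 5 points is the relevant difference. Adjustment multiplies the required number by 1 − ρ²: 146.5 × 0.91 gives 134 robotic patients at ρ = 0.3, and 146.5 × 0.64 gives 94 at ρ = 0.6.

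**The case against.** The best reply is that both lists are introduced as examples, so nothing is excluded. In addition, a treatment model for one substudy and a general outcome-adjustment list for the whole study may legitimately differ. Both parts stand. A reader might infer that the protocol rules comorbidity and calendar time out of the primary analysis, and the text does not say so. What remains is that following the named set leaves out a variable that the sponsor lists elsewhere for adjustment. An open-ended list in a non-randomized primary analysis also leaves the choice of covariates unsettled.

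Four further readings go beyond the documents:
- *Robotic patients are healthier, so the bias favours the robot.* Nothing in the protocol gives the direction of selection.
- *Calendar time does confound.* It does so only if reoperation risk also changes over the four years, which the protocol does not address. The documents establish only its link to treatment.
- *The EQ-VAS analysis is wrong.* The protocol is silent on that model, and a statistical analysis plan may supply the baseline term. That baseline EQ-VAS is the strongest predictor is not shown either.
- *Spinal region is a further gap.* Diagnosis and levels may capture part of it, and the text gives no basis for a separate point.

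It is also fair to object that comorbidity cannot be called data already in hand. Table 1 names no source for it, and only its listing in Section 20 implies that it will be available.

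**Conclusion.** The point holds for comorbidity and calendar time in the propensity score of the primary reoperation analysis. Comorbidity is the firmer of the two, because the protocol's own sections differ on it. Calendar time rests on the staggered arrival of robots together with hospital effects that are fixed over time.

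The size of any bias cannot be derived from the documents. Under the assumed prevalences and risk ratios, comorbidity could contribute about 0.1 to 1.1 percentage points at a 5% rate, before allowing for the covariates already matched, against the 2-point target. No size can be put on calendar time. Baseline EQ-VAS is an improvement to a secondary analysis and not an error in the plan. The change should be made because it is cheap and protects the primary comparison, not because a material bias has been shown.

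**What to change.** - Add comorbidity and calendar period of surgery to the named propensity-score covariates, and include both in the SMD balance check.
- Reconcile this set with Section 20 using pre-treatment variables only. Do not simply merge the two lists. Robotic system type and navigation or freehand use are defined by treatment arm, so in a propensity score for robotic versus non-robotic surgery they would predict the arm perfectly and destroy overlap.
- Name the data source for comorbidity, which Table 1 does not do.
- As a secondary improvement, include preoperative EQ-VAS as a covariate in the 1-year EQ-VAS and PASS comparisons. It is already collected.

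The cost is mainly wording, a few more model parameters, possibly slightly fewer matches (not calculated here), and whatever work the comorbidity source requires. The stated sample sizes need not change.

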Robotic-assisted surgery (RAS) represents a further step in this evolution. These systems, which use a navigated robotic arm to assist screw placement, aim to enhance accuracy and reduce variability—which may be especially beneficial for less experienced surgeons. RAS may also streamline intraoperative workflow and support minimally invasive approaches. While early results are promising, there remains limited evidence on the broader clinical benefits, especially during the early learning phase of implementation [4]. Robotic-assisted spine surgery is not sanctioned by the Swedish Association of Authorities and Regions, unless performed in clinical trials.

This study aims to evaluate the clinical introduction of robotic systems in spine surgery, focusing on their impact on reoperations, screw placement accuracy, complications, outcome, and intraoperative workflow.

7. Objectives

This study has three main objectives, analysed in three different substudies: To study screw placement accuracy, learning curve, and reoperations.

Secondary Objectives: To assess complications, patient-reported outcomes, length of stay, surgical time, and cost-effectiveness.

8. Trial Design

Multicenter, non-randomized observational cohort study with consecutive patient inclusion.

9. Study Setting

All hospitals in Sweden performing spinal surgery will participate.

10. Eligibility Criteria

Inclusion Criteria:

- Treatment with pedicle screws in the cervical, thoracic, lumbar spine and/or sacrum.
- All ages and spinal diagnoses

Exclusion Criteria:

- Treatment without pedicle screws

Consent

-All patients will be treated according to each hospital's routine. Patient consent will therefore not be needed.

11. Interventions

Experimental Group: Robotic-assisted pedicle screw insertion using available equipment. Currently available systems are Brainlab Cirq and Mazor Robotics, but others systems may be used.

Control Group: Patients undergoing non-robotic-assisted (freehand or navigation-assisted) pedicle screw placement.

12. Outcomes

Primary objectives and outcomes

Substudy 1 primary outcome - Screw placement accuracy (binary per-patient outcome)

- Proportion of patients in which at least one screw is not accurately placed.

Substudy 2 primary outcome- Learning curve (surgical time)

-To evaluate when time in surgery is no longer decreasing in robotic-assisted surgery.

Substudy 3 primary outcome - Reoperation rate at 2 years

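### Hospital fixed effects in the Substudy 3 propensity score reduce the matched comparison to the robot hospitals, distort the caliper, invalidate whole-cohort weighting and leave the 80% power claim unsupported

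*Protocol*

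**What the plan says.** Protocol section 9 (Study Setting) states that "All hospitals in Sweden performing spinal surgery will participate". Section 15 (Recruitment) says "Currently robotic-assisted spine surgery is available in two hospitals", with a third waiting for its equipment. It adds: "If other hospitals install robotic-assisted surgery during the study period this will just result in more patients involved in the robotic-assisted arm".

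Section 14, Substudy 3, estimates the propensity score by logistic regression. The covariates include "surgical approach (minimally invasive vs. open), interbody device use, and fixed effects for hospital site". The primary analysis is 1:2 nearest-neighbour matching without replacement, with a caliper of 0.2 standard deviations of the logit score. In the secondary analysis, with stabilized weights, "IPW will be used to create a pseudo-population in which treatment assignment is independent of observed covariates".

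On size, the section says "We estimate a ratio of 1:6 for robotic-assisted surgery vs navigation-assisted or free hand surgeries". It gives 420 + 2,520 patients for 1% vs 3% reoperations and 866 + 5,196 for 3% vs 5%, each at 80% power. It projects 7,200 patients in four years without a split by hospital. It expects propensity methods to cost only a little effective sample size and says that no patient is left out of the final analysis. Overlap weights or trimming are an option, to be looked at if the weights prove unstable.

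**The concern.** A hospital with no robotic case has a robotic-surgery probability of exactly zero. Its fixed effect predicts treatment perfectly, so the coefficient runs off towards minus infinity and the fitted scores go to zero. More patients do not cure this.

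Four things follow. The matched analysis drops every control from those hospitals, although the text implies that all patients count. The caliper is expressed in a standard deviation that the diverging logits dominate. The weighted pseudo-population cannot be independent of hospital when some hospitals have no treated patient. The power statement relies on controls that the primary analysis will not use. At stake are the population to which the main reoperation result applies, the validity of the weighted analysis, and the planned size.

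**Working it through.** **1. Reproducing the plan's sample sizes.** Inputs from section 14: alpha 0.05 (taken as two-sided), 80% power, ratio 1:6. On the arcsine scale, h = |2·arcsin√p1 − 2·arcsin√p2| and n(robotic) = (1.96 + 0.84)²·(1 + 1/6)/h², where (1.96 + 0.84)² is 7.849 before rounding.

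- 1% vs 3%: h = 0.1478, n = 7.849 × 1.1667/0.02185 = 419.0, rounded up to 420.
- 3% vs 5%: h = 0.1029, n = 7.849 × 1.1667/0.01058 = 865.5, rounded up to 866.

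Both figures are reproduced, so the planned size counts all six controls per robotic patient.

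**2. Power under the specified 1:2 matching.** Power = Φ(h/√(1/n1 + 1/n2) − 1.96).

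| Robotic + matched controls | 1% vs 3% | 3% vs 5% |
|---|---|---|
| 420 + 840 | 70% | – |
| 866 + 1,732 | – | 70% |
| 1,029 + 2,058 | 97% | 77% |

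The last row takes one-seventh of the projected 7,200. For 80% power at a full 1:2 match, the same formula with (1 + 1/2) gives 539 + 1,078 and 1,113 + 2,226. The drop from 80% to 70% comes from using two controls instead of six. Hospital effects do not cause it.

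**3. Whether 1:2 matching can be filled.** Let s be the robot hospitals' share of all patients. The protocol does not give s, so the values below are assumptions. I also assume that the 7,200 covers all participating hospitals. Controls at robot hospitals per robotic patient = (s − 1/7)/(1/7) = 7s − 1, which reaches 2 at s = 3/7 = 43%. The share of controls elsewhere is (1 − s)/(6/7).

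| s | Controls elsewhere | Controls per robotic patient at robot hospitals | Power at 420 or 866 robotic | Power at 1,029 robotic (1% vs 3%; 3% vs 5%) |
|---|---|---|---|---|
| 30% | 82% | 1.1 | 59% | 93%; 67% |
| 40% | 70% | 1.8 | 68% | 97%; 75% |
| 43% or more | 66% or less | 2 or more | 70% | 97%; 77% |

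At s = 20% there are 0.4 controls per robotic patient. At least 60% of robotic patients then go unmatched, and power at the stated robotic numbers is about 27%. All rows assume that every available control finds a match, so they are upper limits.

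**4. Weights.** Take s = 30% as an example. A control with score zero gets the stabilized weight (6/7)/(1 − 0) = 0.86, which is unremarkable. There are 0.70 × 7,200 = 5,040 such controls, carrying 5,040 × 6/7 = 4,320 of a total control weight of about 6,171. That is 70%, from hospitals with no robotic patient. Stabilized treated weights should sum to about 1,029. They can only represent the 2,160 robot-hospital patients, so they sum to about 2,160/7 = 309.

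A simulation with 12 hospitals, 3 of them with robots and 30% of volume (all assumed), agreed. Scores elsewhere were below 1e-8, 70% of control weight was off-site, treated weights summed to about 302 for 1,009 robotic patients, and the largest weight was 4.1.

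**5. Caliper.** If the standard deviation is taken over everyone in the fitted model, the 0.2-SD caliper in the 12-hospital example is about 1.9 logits, against 0.09 among robot hospitals alone. The latter implies a standard deviation of 0.09/0.2 = 0.45, so the working caliper spans about 1.9/0.45 = 4 standard deviations and excludes almost no pair there. In a 20-hospital example run with a different stopping rule the values were 2.4 and 0.08. The width depends on when the software stops iterating.

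**The case against.** The strongest reply is that the primary analysis survives. Controls at hospitals without a robot simply go unmatched. Robotic patients are then compared with controls at robot hospitals, which is a valid effect in the treated and close to what one would choose on purpose. This stands. A reader might infer that the matched analysis fails, but the protocol's method does not imply that.

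A reader might also infer that the model cannot be fitted. With a standard deviance stopping rule, the simulated 12-hospital fit stopped normally at iteration 19. Scores at robot hospitals agreed to within 1e-14 with a model fitted there alone. Separation harms the off-site scores and the caliper's scale, not the scores that matter.

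A third tempting reading is that power is simply 37% to 68%. The documents do not support that as a finding. It needs an unstated volume share and holds robotic numbers at 420 or 866 although more may accrue. At its low end it also keeps robotic patients whom matching would drop. Part of the loss is due to 1:2 matching alone.

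The protocol also has safeguards: match yield, balance and weight diagnostics, with overlap weights in reserve. Overlap weights would give zero-score controls no weight, so the remedy is already named. It is optional, however, and tied to unstable weights, which zero-score controls do not produce, so the trigger would probably not fire. The statement that all patients are kept sits beside multiple imputation and may have been meant only for missing covariates, but as written it conflicts with caliper matching. Further robot installations would ease the problem without removing it in hospitals that stay without a robot.

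**Conclusion.** The point holds. The score, caliper, weights and power statement in section 14 do not fit a cohort in which most hospitals may never use a robot. The primary analysis is in effect a within-robot-hospital comparison, valid but not declared as such. Its caliper is far too wide there if scaled on the whole cohort. The whole-cohort weighted effect is not identified, because positivity fails.

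The 80% power is not what the specified matching delivers at the stated robotic numbers: it gives at most about 70%, at any volume share. With 1,029 robotic patients the shortfall depends on the scenario. There is none for 1% vs 3% if matching is full, and power is about 77% for 3% vs 5%. Power figures below the full-match values rest on the assumed share s. The caliper figures rest on simulated examples. All power values use a two-proportion approximation to the planned Cox analysis.

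**What to change.** - Define the primary Substudy 3 population as patients in hospitals that use both techniques, from each hospital's first robotic case. Do not add those hospitals' pre-robot patients as controls: they bring calendar-time confounding and may predate enrolment.
- Fit the propensity score with hospital effects, and compute the caliper, in that population only.
- Make overlap weights, or restriction to these hospitals, the prespecified weighting analysis instead of an optional fallback.
- Replace the statements about a small loss of sample size and about including every patient with the expected match yield and power, by scenario, from those hospitals' own volumes.
- Use the other hospitals only in a labelled secondary analysis without hospital fixed effects and with hospital-clustered standard errors. State that hospital differences remain uncontrolled there.

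The cost is protocol wording and a recalculation. No new data are needed. The stated usable sample becomes smaller and the stated power less favourable.
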